4.2.5 Lost to Follow-Up

A participant will be considered lost to follow-up if he or she fails to return for scheduled visits or is unable to be contacted by the study site.

The following actions must be taken if a participant fails to return to the clinic for a required study visit:

- The site must attempt to contact the participant and reschedule the missed visit as soon as possible and counsel the participant on the importance of maintaining the assigned visit schedule and ascertain whether the participant wishes to and/or should continue in the study.
- Before a participant is deemed lost to follow-up, the Investigator or designee must make every effort to regain contact with the participant (where possible, 3 telephone calls over a 4-week period and, if necessary, a certified letter to the participant's last known mailing address or local equivalent methods). These contact attempts should be documented in the participant's study file.

If the participant continues to be unreachable, he/she will be considered to have withdrawn from the study.

4.2.6 Replacements

Participants who withdraw from the study after randomization may be replaced.

4.3 Discontinuation of Study

Although the Sponsor has every intention of completing the study, the Sponsor reserves the right to discontinue the study at any time for clinical or administrative reasons.

The end of study (EOS) is defined as the date on which the last participant completes the last study visit (including the EOS visit and any additional long-term follow-up). Any additional long-term follow-up that is required for monitoring of the resolution of an AE or finding may be appended to the clinical study report (CSR).

5 STUDY TREATMENTS

5.1 Method of Assigning Participants to Study Groups

Participants will be randomized after all Screening assessments have been completed and after the Investigator has verified that they are eligible per criteria in Sections 4.1.1 and 4.1.2. No participant may begin study treatment prior to randomization and assignment of a unique participant identification number.

The Sponsor or designee will prepare the randomization list, which will be provided to the study site unblinded pharmacist.

5.2 Study Vaccine, Dosage, and Route of Administration

ARCT-165, ARCT-154, and ARCT-021 study vaccines are LNP-formulated, RNA replicon vaccines. Details of the RNA composition of each study vaccine are described in Section 1.4.

The nanoparticle composition includes 4 lipid excipients (ionizable cationic lipid; Arcturus proprietary lipid; neutral lipid, 1,2-distearoyl-sn-glycero-3-phosphocholine [DSPC]; cholesterol; and polyethylene glycol-lipid conjugate).

The study vaccines are provided as lyophilized formulations in multi-dose glass vial presentations. The diluent for administration consists of 0.9% sodium chloride for injection, United States Pharmacopeia (USP), British Pharmacopeia (BP) or equivalent, and preservative-free. Sodium chloride (0.9%) will be provided by the study site.

The study vaccines will be prepared by an unblinded trained site staff member in accordance with the Pharmacy Manual and outside of the view of blinded team members. The dose for administration to Cohorts A and B for all 3 study vaccines is 5 μ g.

Study vaccines will be matched for volume (0.5 mL) and presentation (1-mL syringe) prior to administration.

Study vaccine (ARCT-165, ARCT-154, or ARCT-021) will be administered by intramuscular (IM) injection to the deltoid muscle by a health care provider (HCP) who will not be involved in assessments of any study endpoints. Study vaccine preparation and administration should be performed in an area outside of the view of blinded team members. Unblinded team members will not otherwise participate in other study-related procedures or assessments of the participant.

The IM injection of the study vaccine will be into the lateral aspect of the deltoid muscle of the non-dominant arm, where possible.

Epinephrine for subcutaneous (SC) injection, diphenhydramine for intravenous injection, and any other medications and resuscitation equipment for the emergency management of anaphylactic reactions must be available in close proximity to the room where the vaccination is administered.

5.3 Management of Clinical Supplies

5.3.1 Investigational Product Packaging and Storage

The Sponsor will provide the Investigator with packaged study vaccine (ARCT-165, ARCT-154, and ARCT-021) containers labeled in accordance with specific country regulatory requirements.

Commercially available 0.9% sodium chloride for injection, USP, BP or equivalent, and preservative-free for dilution will be provided by the site. See the Pharmacy Manual for additional guidance.

The study staff is required to document the receipt, dispensing, and return/destruction of study vaccine (ARCT-165, ARCT-154, and ARCT-021) supplies provided by the Sponsor. The study site must destroy or return for destruction all unused frozen vials of study vaccine (ARCT-165, ARCT-154, or ARCT-021) to the Sponsor or designee. Vials of study vaccine (ARCT-165, ARCT-154, or ARCT-021) should be destroyed by the study site or delegate only after drug accountability has been done by the unblinded study monitor. Destruction or return of study vaccine must be documented.

Study vaccine temperature storage requirements and monitoring procedures are included within the Pharmacy Manual.

5.3.2 Study Vaccine Accountability

The Investigator will maintain accurate records of receipt of all study vaccines (ARCT-165, ARCT-154, and ARCT-021) and diluent, including dates of receipt. In addition, accurate records will be kept regarding when and how much study vaccine is administered to each participant in the study. Only participants enrolled in the study may receive any study vaccine, and only authorized site personnel may supply or administer the study vaccine. Reasons for departure from the expected dispensing regimen must also be recorded. At the completion of the study, to satisfy regulatory requirements regarding drug accountability, all study vaccines will be reconciled and destroyed according to applicable regulations. Further guidance and information for the final disposition of unused study vaccines are provided in the Pharmacy Manual.

5.3.3 Other Supplies for Participant Use

Study sites will distribute Sponsor-provided thermometers for body temperature measurement and rulers to measure injection site erythema and induration/swelling reactions. The measurements will be captured in the paper Diary Card provided by the site.

5.4 Overdose Management

Study vaccine errors (including overdose, underdose, and administration error) must be documented as protocol deviations. A brief description should be provided of the deviation, including whether the participant was symptomatic (list symptoms) or asymptomatic, and whether the event was accidental or intentional.

Dosing details should be captured on the appropriate source documents and on the Dosing eCRF.

An overdose is the accidental or intentional administration of a study vaccine in an amount higher than the dose being studied. An overdose or incorrect administration of study vaccine is not itself an AE, but it may result in an AE. If the participant receives a dose of study vaccine that exceeds protocol specifications and the participant is symptomatic, the symptom(s) should be documented as an AE (Section [6.3.1.2](#)).

Should an overdose occur, the Investigator or designee should contact the Sponsor or designee within 24 hours.

There are no known treatments for potential overdose of study vaccine. Unless there is a user error leading to failure to administer any volume of study vaccine, “catch-up” study vaccine administrations will not be performed.

5.5 Blinding

The study vaccines will be administered in an observer-blind fashion.

Each of the study vaccines will be prepared by an unblinded trained team member and in accordance with the Pharmacy Manual.

Unblinded personnel (of limited number) will be assigned to study vaccine accountability procedures and will prepare study vaccine for all participants. These personnel will have no study functions other than study vaccine management, documentation, accountability, preparation, and administration. They will not be involved in participant evaluations and will not reveal the identity of study vaccine to either the participant or the blinded study site personnel involved in the conduct of the study unless this information is necessary in the case of an emergency.

- The HCP who administers the study vaccine will not be involved in assessments of any study endpoints.
- Unblinded site monitors not involved in other aspects of monitoring will be assigned as the study vaccine accountability monitors. They will have responsibilities to ensure that sites are following all proper study vaccine accountability, preparation, and administration procedures.

In order to maintain an observer-blind design, Investigators, site staff, participants, and CRO staff with oversight of study conduct will remain blinded to study vaccine assignments for the study duration. The Sponsor team with direct oversight of the study will remain blinded to individual participant study vaccine assignments until the time of study unblinding at the final analysis. All study participants will be followed for efficacy and safety endpoints through the planned study period, and results will be summarized in an EOS report.

Sponsor staff who are not involved in direct oversight of the study may receive unblinded study data but will not share any unblinded information with the Sponsor team members overseeing the study.

5.5.1 Breaking the Blind

An individual participant’s study vaccine assignment will not be unblinded to the Investigator or other blinded study site staff until the EOS unless awareness of the study vaccine assignment is relevant to the care of study participant. If the blind needs to be broken because of a medical emergency, the Investigator may unblind an individual participant’s treatment allocation.

To the extent possible before unblinding, the Investigator should contact the Medical Monitor to discuss the medical emergency and the reason for revealing the actual treatment received by that participant. The study vaccine assignment will be unblinded through review of the randomization list provided to the study site unblinded pharmacist. Reasons for unblinding must be clearly explained and justified in the eCRF. The date on which the code was broken together with the identity of the person responsible must also be documented.

Participants who choose to receive vaccination with off-study COVID-19 vaccine will be encouraged to remain in the study, but those that choose to leave the study to pursue alternate vaccination will not be unblinded to study treatment unless there is an unexpected post-study SAE attributed as related to study vaccine by the study Investigator and for which the Investigator feels that awareness of the study vaccine assignment is relevant to the care of study participant.

5.6 Compliance with Study Treatment

When participants are dosed at the site, they will receive the study vaccine directly from designated study site staff under medical supervision. The date and time of each dose administered will be recorded in the source documents and recorded in the eCRF. The receipt of study vaccine and study participant identification will be confirmed at the time of dosing by a member of the study site personnel other than the person administering the study vaccine.

5.7 Concomitant and Rescue Therapies and Procedures

The use of concomitant therapies or procedures defined in the following section must be recorded on the participant's eCRF. AEs associated with administration of these therapies or procedures must also be documented on the appropriate eCRF.

5.7.1 Concomitant Therapy

Study site staff must question the participant regarding any medications taken (including herbal/homeopathic substances) and vaccinations received by the participant. The following information will be recorded in the eCRF:

- Concomitant, non-study vaccinations administered as early as 28 days prior to receipt of the first dose of study vaccine and throughout the duration of study participation.
- Concomitant medications and procedures are to be collected from Screening until 28 days after receipt of the last dose of study vaccine and if associated with an unscheduled visit. Concomitant medications and procedures associated with SARS-CoV-2 infection/COVID-19, SAEs, medically attended adverse events (MAAEs), and AEs leading to discontinuation of study vaccine/ study withdrawal are to be collected through EOS participation.
- Participants will be asked prior to vaccination and will be asked for 7 days after each vaccination in the paper Diary Card if they have taken any antipyretic or analgesics to prevent or treat study vaccine-associated side effects (AEs). Reported antipyretic or analgesic medications should be recorded in the source document by the site staff during the study visits or via other participant interactions (e.g., telephone calls).

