5.7.2 Prohibited Concomitant Vaccines and Concomitant Therapy

Receipt of non-study COVID-19 vaccine is prohibited for all enrolled participants while on study. Participants in Cohort B must have received both doses of BNT162b2 vaccine at least 5 months prior to study enrollment.

The use of the following concomitant medications and/or vaccines will not require withdrawal of the participant from the study but may determine a participant's eligibility to receive a second dose or evaluability in the per-protocol analysis:

- Any investigational or non-registered product (drug or vaccine) other than the study vaccine used during the study period.
- A non-study, live, attenuated vaccine administered during the period from 28 days before through 28 days after each dose of study vaccine or any approved inactivated or recombinant vaccine that was administered within 14 days before or after any dose of study vaccine.
- Immunoglobulins and/or any blood products administered during the study period (except for treatment of COVID-19).
- Medications that suppress the immune system, including corticosteroids administered at doses of 20 mg prednisone equivalent/day or higher, with the exception of medications used in the treatment of COVID-19.

Section 4.2.1 describes delay in vaccination that will occur in the event of analgesic/antipyretic use prior to planned study vaccination.

If a participant receives/takes a prohibited vaccine or drug therapy, the Investigator and the CRO's Medical Monitor will make a joint decision about continuing or withholding further dosing from the participant based on the time the medication was administered, the drug's pharmacology and pharmacokinetics, and whether use of the medication will compromise the participant's safety or the interpretation of data. It is the Investigator's responsibility to ensure that details regarding concomitant medications and vaccines are adequately recorded in the eCRF. All medication and interventions necessary for the appropriate care for the study participant, particularly to treat COVID-19, should be administered and appropriately documented along with the AE.

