6.3.1.2.3 Medically Attended Adverse Events

An MAAE is an AE that leads to an unscheduled visit (including a telemedicine visit) with an HCP (e.g., nurse, nurse practitioner, physician's assistant, physician). This would include visits to a study site for unscheduled assessments (e.g., rash assessment, abnormal laboratory follow-up, COVID-19) and visits to HCPs external to the study site (e.g., urgent care, primary care physician).

- Routine study visits will not be considered medically attended visits.
- AEs observed in the immediate 30-min post-vaccination observation period will be regarded as MAAE if:
 - Treatment of the AE is required prior to discharge OR
 - Extension of observation is required due to clinical concerns or unstable clinical findings

Investigators will review unsolicited AEs for the occurrence of any MAAEs. All MAAEs must be reported in the eCRF.

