7.5.4 Immunogenicity Analyses

Analyses will be conducted using the Immunogenicity set as defined for the specific assay under evaluation. Immunogenicity endpoints are described in Section 2 and will be summarized, by study vaccine group and time point, using descriptive statistics. If formal statistical testing is performed, it will be described in the SAP.

The kinetics of immune response following vaccination with each study vaccination will be evaluated in binding, neutralizing antibody responses, and CMI through 365 days after the last vaccination.

Participants who have a nucleocapsid (N) binding antibody test that is positive during the study will be identified, and sensitivity analyses of the immunogenicity data will be conducted with and without participants with this positive test.

A full description of planned analyses for immunogenicity endpoints will be contained in the SAP prior to the time of the intended analysis.

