4.6.5.5 Prior and Concomitant Therapies/Medications

Medications will be coded using the World Health Organization Drug Dictionary Enhanced (WHODDE), version Global-B3 March 2021. Medications entered on the eCRF will be mapped to Anatomic Therapeutic Chemical (ATC) drug class (level 4) and drug name.

Prior and concomitant medications will be summarized separately and the study phase of each medication will be determined programmatically based on medication start and end dates. A prior medication is defined as any medication administered prior to the date of the first study vaccine administration. A concomitant therapy includes non-study vaccinations administered within the period starting 28 days before the first administration of study vaccine and for the duration of study participation. A concomitant medication is defined as any medication administered on or after the date of the first study vaccine administration through Day 28 following the last vaccination. A medication may be defined as both prior and concomitant. If it cannot be determined whether a medication was received prior to the first study vaccine administration due to partial or missing medication start and/or end dates, it will be considered a prior medication. Likewise, if it cannot be determined whether a medication was received after the first study vaccine administration, it will be considered concomitant.

For both prior and concomitant medications summaries, the number and percentage of participants receiving any medication will be summarized by study vaccine group, as will the number and percentage receiving any medication by ATC drug class and generic drug name. Prior medications will also be summarized over all participants combined. Participants reporting use of more than one medication at each level of summarization (any medication received, ATC class, and generic drug name) will be counted only once. ATC class terms will be displayed by descending order of incidence, as will generic drug names within each ATC class. The study phase during which each medication was received (e.g., prior, concomitant, or both) will be presented on the listing of prior and concomitant medications.

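### After 28 days post last dose, the immune-active products restricted in Protocol 5.7.2 are recorded only when linked to a qualifying event, so screening for them is incomplete at 4 of 8 (Cohort A) and 4 of 6 (Cohort B) post-dose antibody visits

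*Protocol*

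**What the plan says.** **Recording window.** Protocol 5.7.1: "Concomitant medications and procedures are to be collected from Screening until 28 days after receipt of the last dose of study vaccine". The sentence goes on: "and if associated with an unscheduled visit". The next sentence extends recording for medications associated with COVID-19, SAEs, MAAEs and certain other events: "AEs leading to discontinuation of study vaccine/ study withdrawal are to be collected through EOS participation". Footnote q of Appendices 1 and 2 repeats these limits. Non-study vaccinations are recorded throughout participation.

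**Restricted products.** Protocol 5.7.2 lists investigational or non-registered products used during the study period. It also lists "Immunoglobulins and/or any blood products administered during the study period (except for treatment of COVID-19"), and immunosuppressive medication with no end date and the same COVID-19 exception. Use does not force withdrawal, but it may bear on a second dose or on "evaluability in the per-protocol analysis".

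**Analysis.** Protocol 7.5.4 plans to describe the kinetics of binding antibody, neutralizing antibody and "CMI through 365 days after the last vaccination". SAP 4.6.5.5: "A concomitant medication is defined as any medication administered on or after the date of the first study vaccine administration through Day 28", counted from the final dose. SAP 4.2 keeps participants with major protocol deviations out of the Immunogenicity Analysis Set (IAS), on the sponsor Medical Monitor's judgement.

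**The concern.** The restriction and the data collection that should support it cover different periods. Two of the three drug classes are restricted for the whole study and the third has no end date, but general recording stops four weeks after the last dose.

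GMC, GMFR and the proportion with a 4-fold rise are primary summaries at every scheduled visit up to Day 394 (Cohort A) or Day 366 (Cohort B). The GMC ratio is also primary for neutralizing antibody. Antibody received passively, or immunosuppression, could be read at a late visit as vaccine-induced persistence or waning. The planned safeguards deal with infection only: censoring before confirmed COVID-19 (SAP 4.5.1) and the analyses by nucleocapsid result (Protocol 7.5.4, SAP 4.8.1.7). Neither would pick up these products.

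**Working it through.** The plan states no figure on this point, so there is nothing to reproduce. The check is a count of visits, followed by a conditional size.

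**1. Cut-off day.** This is the last dose day plus 28.
- Cohort A (Protocol 6.2.1, last dose Day 29): 29 + 28 = Day 57.
- Cohort B (Protocol 6.2.2, Day 1): 1 + 28 = Day 29.

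**2. Post-dose antibody visits after the cut-off.**
- Cohort A, from Days 15, 29, 43, 57, 119, 209, 299 and 394: Days 119, 209, 299 and 394, so 4 of 8.
- Cohort B, from Days 15, 29, 91, 181, 271 and 366: Days 91, 181, 271 and 366, so 4 of 6.
- A last dose one day late moves the cut-offs to Days 58 and 30 and changes neither count.
- T-cell sampling (Appendices 1 and 2): Days 209 and 394 (2 of 6 post-dose) in Cohort A; Days 181 and 366 (2 of 4) in Cohort B.

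**3. Length of follow-up with event-linked recording only.** 394 − 57 = 337 days and 366 − 29 = 337 days. As a share of the 365 days after the last dose, 337/365 = 92%.

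**4. What the triggers miss.** Protocol 6.3.1.2.3: "An MAAE is an AE that leads to an unscheduled visit (including a telemedicine visit) with an HCP". A steroid course from a routine appointment, planned immunoglobulin or an investigational drug from another study need not involve an unscheduled visit or any of the listed events. An investigational vaccine should still be caught, because vaccinations are recorded throughout.

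**5. SAP category.** SAP 4.6.5.5 has two classes: prior (before the first dose) and concomitant (first dose to Day 28 after the last). A drug started later is in neither, even when 5.7.1 required its collection. It has no place in the tables and no study phase in the listing.

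**6. Conditional size.** SAP 4.1.4 defines the GMC as the antilog of the mean log10 value. If one participant's titre changes by a factor k, the GMC of n participants changes by k^(1/n). The GMFR changes by the same factor if the baseline value is unaffected. Planned group sizes are 12/3 = 4 (A1), 24 × 1/4 = 6 and 24 × 3/4 = 18 (A2), and 36/3 = 12 (Cohort B). The range k = 3 to 10 is my assumption.

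| Group | n | k = 3 | k = 10 |
|---|---|---|---|
| A1, each vaccine | 4 | 1.32 | 1.78 |
| A2, ARCT-021 | 6 | 1.20 | 1.47 |
| Cohort B, each vaccine | 12 | 1.10 | 1.21 |
| A2, ARCT-154 | 18 | 1.06 | 1.14 |

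One participant crossing the 4-fold threshold moves that proportion by 1/n, which is 25 percentage points at n = 4. Losses before the late visits would make n smaller and the shifts larger.

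**The case against.** A reader might infer that the late visits cannot be screened at all, or that 337 days go unrecorded. The documents do not support this. Drugs tied to COVID-19, an SAE, an MAAE, an AE leading to discontinuation or withdrawal, or any unscheduled visit are collected to the end of participation. The MAAE definition is broad: telemedicine and outside providers count, and most new illnesses needing these drugs would probably meet it. Eligibility narrows the gap further by excluding autoimmune disease, immunodeficiency, immunomodulators, immunoglobulin or blood products during the study, and planned participation in another investigational study.

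Other routes exist. Medications are asked about at every late visit, Protocol 5.7.2 makes the Investigator responsible for adequate eCRF recording, and Protocol 11.2.2 requires deviations to be documented in source. So it also goes too far to say that the Medical Monitor has no means of applying the IAS rule. These routes still do not close the gap. Footnote q limits what the interview collects, the general duty has no time span and does not override the stated cut-off, and a deviation must first be noticed.

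Nor are late-collected drugs lost, because SAP 4.1.1 puts all collected data in listings. For COVID-19 treatment the missing category matters little to immunogenicity: results are already censored before confirmed infection, and 5.7.2 exempts such treatment from the immunoglobulin and immunosuppressant restrictions.

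On size, the 3- to 10-fold range has no source in the documents, and sampling error is larger. With an assumed log10 SD of 0.3 to 0.5, the planned t interval divides and multiplies the GMC by 10^(t × SD/√n). That is 3.0 to 6.2 at n = 4 (t = 3.182), 2.1 to 3.3 at n = 6 (t = 2.571) and 1.55 to 2.1 at n = 12 (t = 2.201). Each exceeds the corresponding shift in the table. This limits the importance of the point, but an interval for sampling error does not reveal a confounded value.

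The 28-day limit also matches the general window for unsolicited AEs (Protocol 6.3.1.2.8), so it may be deliberate. That would justify it for ordinary medications, but not for classes that 5.7.2 ties to evaluability beyond that window.

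**Conclusion.** The mismatch stands. For 4 of 8 antibody visits in Cohort A and 4 of 6 in Cohort B, the 5.7.2 products are recorded only through event-linked triggers, so screening at those visits is incomplete. The residual gap is restricted use with no qualifying event or unscheduled visit. The documents give no rate for it, so its actual effect on the late GMC and GMFR cannot be estimated. The factors in the table hold only if such a case occurs, under the assumed 3- to 10-fold change and full planned group sizes.

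Two further points do not depend on how often the products are used. SAP 4.6.5.5 gives later-started drugs no category. The per-protocol analysis named in 5.7.2 is defined in neither document; taken alone this is a labelling matter, since the IAS already does that job. In a descriptive study this is an inexpensive improvement worth making, not a threat to the study's conclusions.

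**What to change.** 1. **Protocol 5.7.1 and footnote q of Appendices 1 and 2.** Reconcile these with 5.7.2 by recording the 5.7.2 drug classes through the Final or Early Termination Visit, at the concomitant-medication interviews already scheduled. Leave other medications at 28 days. All 8 and all 6 post-dose antibody visits would then be covered.
2. **SAP 4.6.5.5.** Add a category for medications started more than 28 days after the last dose, so that those validly collected are tabulated, separately from earlier ones.
3. **Protocol 5.7.2 and SAP 4.5.1.** Refer to the Immunogenicity Analysis Set in place of the undefined per-protocol analysis. Add a sensitivity summary that drops a participant's results only from the date a 5.7.2 product started and keeps earlier visits.

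The cost is a short amendment, a few extra eCRF entries and one extra run, with no new visit or procedure. The limitation is timing. Preliminary Cohort B data were already cited in the rationale for Sub-cohort A2 introduced in Protocol Version 3.0 (March 2022), and the latest amendment listed is Version 4.0 (August 2022). For Cohort B visits already completed, the information can only be sought retrospectively, and the report should say so.
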